6.10.4.5. Pancreatitis

Summaries of adjudicated and investigator-reported pancreatic events will be provided by each randomized treatment. However, the summary report will only be generated if >3% patients have pancreatic event(s). Determination of investigator-reported events will be through the “Acute pancreatitis” SMQ and a “Chronic pancreatitis” Lilly Search Categories (LSC) of the AE database, while adjudication-confirmed pancreatitis will be found from adjudication CRF.

The patients developing pancreatitis will be listed separately for the investigator-reported and the adjudicated events.

Each pancreatic enzyme at Week 12, and the maximum post-dose value will be summarized by each randomized treatment in a shift table using $>1\times$ the upper limit of normal (ULN), and $\geq 3\times$ ULN separately for the mITT population, mITT population with normal baseline, mITT population with baseline value $>ULN$.

6.10.4.6. C-cell Hyperplasia and C-cell Neoplasms

Listings of AEs of interest using a LSC will be provided by High-Level Terms (HLTs) thyroid neoplasms, thyroid neoplasms malignant, and thyroid disorders. The summary report for these AESIs by each randomized treatment will be reported if there are >3% patients with these AESIs.

Calcitonin data will be summarized using an ANCOVA model similar to the supportive analyses.

Calcitonin values will be listed for those patients with a post-first-dose serum calcitonin increase from baseline $\geq 50\%$ and the absolute value ≥ 20 pg/mL. These patients will be classified by their absolute calcitonin values into the following categories: ≥ 20 and < 35 pg/mL; ≥ 35 and < 50 pg/mL; and ≥ 50 pg/mL. A shift table using these categories will be generated if the proportion of patients with these changes is $> 3\%$.

6.10.5. Laboratory Measurements

Laboratory measurements will be summarized by treatment group using descriptive statistics at each scheduled time of assessment during the treatment and follow-up periods and including any off-treatment safety follow-up visits that occur after discontinuation of study treatment.

Descriptive statistics for laboratory analyses with continuous results will include sample size, mean, SD, median, minimum, and maximum for both actual values and change from baseline.

Laboratory analyses with categorical responses will be summarized by visit and treatment group using sample size, frequency, and percentage.

A listing of laboratory measurements for individual patients will be presented by visit. An additional listing will be presented for all laboratory measurements that are outside the normal range. All laboratory measures that meet the criteria for a listing will be reported, including unscheduled and repeat or multiple measurements.

A summary report and analysis for treatment-emergent abnormal laboratory values (outside the reference ranges as appropriate) will be provided for each continuous analyte by treatment. Shift tables of the change from baseline value to the maximum/minimum postbaseline value to Week 12 for selected analytes using clinically meaningful thresholds will be summarized. A shift table for alanine aminotransferase (ALT), aspartate aminotransferase (AST), total bilirubin, and direct bilirubin will be generated using cutoff $\leq 1 \times \text{ULN}$, $> 1 \times \text{ULN}$ and $< 3 \times \text{ULN}$, $\geq 3 \times \text{ULN}$ and $< 5 \times \text{ULN}$, $\geq 5 \times \text{ULN}$ and $< 8 \times \text{ULN}$, $\geq 8 \times \text{ULN}$.

A listing of ALT, AST, and total bilirubin values at all visits will be presented for all patients who meet any of the following criteria:

- ALT $\geq 3 \times \text{ULN}$
- AST $\geq 3 \times \text{ULN}$
- total bilirubin $\geq 2 \times \text{ULN}$
- ALT or AST $\geq 3 \times \text{ULN}$ and total bilirubin $\geq 2 \times \text{ULN}$.

6.10.6. Electrocardiograms

For ECG parameters that collected in triplicates, the arithmetic mean from the 3 measures for the same parameter at the same visit will be calculated and use for all subsequent analyses. This will include ECG heart rate (HR) in beats per minutes (bpm), QRS complex (milliseconds [msec]), and PR interval (msec), as well as the time elapsed between the onset of ventricular depolarization and the end of ventricular repolarization (QT) and QT corrected by heart rate (HR) values using Fridericia's formula (QTcF). Fridericia's correct QT formula will be reported in (msec). Descriptive statistics for the absolute values and changes from baseline for the ECG

parameters (HR, PR interval, QRS, QT, QTcF) will be presented by treatment arm. Additional summary statistics will be provided for abnormal values (categorized as Low or High as shown in Table 6.5). An MMRM-based model similar to the analysis of the primary outcome will also be used for the change from baseline in HR, PR, and QTcF.

Table 6.5. Electrocardiogram Abnormal Categories

Measure	Low	High
PR Interval	<120 msec	≥220 msec
QRS Interval	<60 msec	≥120 msec
HR	<50 and decrease of ≥15 bpm	>100 and increase ≥15 bpm
QT	NA	>500 msec
QTcF	NA	>450, >480, and >500 msec

Abbreviations: bpm = beats per minute; HR = heart rate; msec = milliseconds; NA = not applicable; QTcF = QT corrected values using Fridericia's formula.

In addition, LY3298176 concentration-response analysis of QTcF and RR results may be performed, using figures that display change from baseline in QTcF on the vertical axis versus LY3298176 concentration (from pharmacokinetics/pharmacodynamics [PK/PD]) on the horizontal axis, time-matched with the QTcF measurements. The figures will also include a regression line and corresponding regression analysis.

Summaries of categories for absolute observations and change from baseline for QTcF intervals will be provided as well, with absolute categories as >450, >480, and >500 msec and change from baseline categories as >30 msec and >60 msec.

6.11. Exploratory Analyses

Baseline will be the measurements prior to treatment for SMBG.

Immunogenicity will be analyzed and summarized.

6.11.1. 7-Point SMBG

The 7-point SMBG profile consists of pre-meal and 2-hour postprandial blood glucose (BG) measurements for morning, midday, and evening meals, as well as a bedtime BG measurement. Analyses will apply to the changes from baseline in the following variables for 7-point glucose profiles:

1. pre-morning meal-fasting BG (mg/dL)
2. morning meal 2-hour (hr) BG (mg/dL)
3. pre-midday meal BG (mg/dL)
4. midday meal 2-hour BG (mg/dL)
5. pre-evening meal BG (mg/dL)
6. evening meal 2-hour BG (mg/dL)

7. bedtime BG (mg/dL)
8. morning meal 2-hour excursion (mg/dL)
9. midday meal 2-hour excursion (mg/dL)
10. evening meal 2-hour excursion (mg/dL)
11. mean of all meals 2-hour excursion (mg/dL)
12. mean of all 7-point BG (mg/dL)
13. mean of all pre-meals BG (mg/dL)
14. mean of all 2-hour postprandial BG (mg/dL).

The morning, midday, and evening meal 2-hour excursions (that is, variable 8 through variable 10) will be calculated for each meal as the 2-hour postprandial BG minus the pre-meal BG.

The change from baseline of 7-point SMBG profiles will be calculated using a similar ANCOVA model to the one used for the supporting analysis for the primary endpoint described in Section 6.9.1.1. The corresponding baseline will be used in the model instead of the baseline HbA1c levels. The ANCOVA model will include a term for the HbA1c stratification group.

6.11.2. Evaluation of Immunogenicity

6.11.2.1. Definitions of Sample Anti-drug Antibody Status

At a high level, an individual sample is potentially examined multiple times, in a hierarchical procedure to produce a sample anti-drug antibodies (ADA) assay result and potentially multiple cross-reactive antibodies assay results and multiple neutralizing antibodies (NAb) assay results. The cut points used, the drug tolerance of each assay, and the possible values of titers are operating characteristics of the assay.

It can be the case that the presence of high concentrations of LY will affect immunoassays, and conversely high levels of antibodies may affect the measurement of LY concentration. Thus, an LY drug concentration, assessed from a sample drawn at the same time as the ADA sample, plays a key role in clinical interpretation of a sample when the laboratory result is Not Detected (Table 6.6).

Table 6.6. Sample Anti-Drug Antibodies (ADA) Assay Results

Sample Laboratory Result	Explanation
Detected	ADA are detected and confirmed.
Not Detected	The raw result as reported from the laboratory indicates not detected. The clinical interpretation of such results depends other factors (see below).
NO TEST, QNS, etc.	Sample exists but was unevaluable by the assay

Abbreviations: QNS = quantity not sufficient.

Table 6.7. Sample Clinical Anti-Drug Antibodies (ADA) Interpretation Results

Sample Clinical Interpretation	Explanation
ADA Present	ADA assay result is Detected
ADA Not Present	ADA assay result is Not Detected and simultaneous drug concentration is at a level that has been demonstrated to not interfere in the ADA detection method (that is, drug concentration is below the assay's drug tolerance level). For patients receiving placebo, drug concentration is not assessed and is assumed to be below the assay's drug tolerance level. If drug concentration was planned but is not available for a treatment-period sample, a Not Detected sample will be declared ADA Inconclusive.
ADA Inconclusive	ADA assay result is Not Detected but drug concentration in the sample is at a level that can cause interference in the ADA detection method.
ADA Missing	ADA sample not drawn, QNS, not tested, etc., causing there to be no laboratory result reported or the result is reported as "no test."

Abbreviations: QNS = quantity not sufficient.

Parallel terminology applies for each type of cross-reactive and NAb. Importantly, each of these are distinct assays and, in general, have different assay operating characteristics.

6.11.2.2. Definitions of Immunogenicity Assessment Periods

Immunogenicity Baseline Observations: Baseline period for immunogenicity assessment for each patient includes all observations on or prior to first administration of study drug. In instances where multiple baseline observations are collected, to determine patient ADA status the last nonmissing immunogenicity assessment prior to first administration of study drug is used to determine treatment-emergent status (see below). In this context, "missing" includes explicit "ADA Missing" results, as defined in [Table 6.7](#).

Immunogenicity Postbaseline Period Observations: Postbaseline period observations for each patient include all observations after the first administration of study drug.

6.11.2.3. Definitions of Patient ADA Status

Patient evaluable for treatment-emergent ADA (TE-ADA): A patient is evaluable for TE-ADA if the patient has a nonmissing baseline ADA result, and at least 1 nonmissing postbaseline ADA result.

Treatment-emergent ADA positive (TE-ADA+) patient: A patient who is evaluable for TE-ADA is TE-ADA+ if either of the following holds:

- The patient has baseline status of ADA Not Present and at least 1 postbaseline status of ADA Present with titer $\geq 2 \times \text{MRD}$, where the MRD is the minimum required dilution of the ADA assay.
- The patient has baseline and postbaseline status of ADA Present, with the postbaseline titer being 2 dilutions (4-fold) greater than the baseline titer. That is, the patient has baseline status of ADA Present, with titer 1:B, and at least 1 postbaseline status of ADA Present, with titer 1:P, with $P/B \geq 4$.

Treatment-emergent ADA Inconclusive patient: A patient who is evaluable for TE-ADA is TE-ADA Inconclusive if $\geq 20\%$ of the patient's postbaseline samples, drawn pre-dose, are ADA Inconclusive and all remaining postbaseline samples are ADA Not Present.

Treatment-emergent ADA negative (TE-ADA-) patient: A patient who is evaluable for TE-ADA is TE-ADA- when the patient is not TE-ADA+ and the patient is not TE-ADA Inconclusive.

6.11.2.4. Analyses to be Performed

The number and proportion of patients who are TE-ADA+ will be tabulated by treatment group, where proportions are relative to the number of patients who are TE-ADA evaluable, as defined above. The tabulation will include the number and proportion of patients with ADA Present at baseline, and also the number and proportion of TE-ADA+ patients exhibiting each type of cross-reactive antibodies and NAb. This analysis will be performed for: (a) the active treatment period; and also for (b) the entire postbaseline period including follow-up.

A listing will be provided of all immunogenicity assessments for those patients who at any time had ADA Present. This includes the LY concentration from a simultaneous PK sample, and the clinical interpretation result (ADA Present, ADA Not Present, ADA Inconclusive, Missing). In the case of ADA Present, a titer will be included, and TE-ADA+ observations will be flagged. Also included, for each cross-reactive antibodies and NAb assay that was performed, will be the clinical interpretation result.

A summary will be provided of the number and percentage of LY-treated patients experiencing specific TEAE (see [Table 6.8](#)) by patient TE-ADA status (TE-ADA+, TE-ADA-, TE-ADA Inconclusive). The PT will be ordered by decreasing incidence in TE-ADA+ status group.

A listing will be provided of all TEAEs alongside ADA data for any patient who had ADA Present at any time (including baseline) or had any specific TEAE (see [Table 6.8](#)). This listing includes a time course of ADA (clinical interpretation result plus flags for samples meeting TE-ADA+ criteria and for samples with cross-reactive antibodies and NAb present) along with the TEAE.

Table 6.8. Adverse Events for Analysis with Immunogenicity Results

Events satisfying Anaphylaxis standardized MedDRA query (SMQ) (narrow or broad)
Events satisfying Hypersensitivity SMQ (narrow or broad)
Events satisfying Angioedema SMQ (narrow or broad)
Events mapping to High-Level Term (HLT) of Injection site reaction
Events mapping to HLT of Infusion site reaction

Abbreviations: MedDRA = Medical Dictionary for Regulatory Activities.

The primary efficacy measure of change in HbA1c from baseline to 12 weeks may be examined in relation to ADA. The initial examination will be boxplots of change in HbA1c at 12 weeks, compared to maximum observed titer (1 category for each titer value) during the active treatment period, for patients who were TE-ADA+ during that period. An additional category will be provided for patients who were not TE-ADA+ during the active treatment period.

Additional immunogenicity analyses as determined later may be presented. The relationship between antibody titers, the PK parameters, and PD response to LY3298176 may also be assessed.

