9.10. Samples for Immunogenicity Research

Samples from all patients will be tested for antidrug antibodies (ADA) against LY3298176. A blood sample will be collected at specific study visits according to the Schedule of Activities (Section 2). All samples for immunogenicity should be taken predose when applicable. To interpret the results of immunogenicity, a PK sample should be collected at the same time point as an the immunogenicity sample. In the event of drug hypersensitivity reactions (immediate or nonimmediate), additional samples will be collected as close to the onset of the event as possible, at the resolution of the event, and 30 days following the event. Instructions for the collection and handling of blood samples will be provided by the sponsor. The actual date and 24-hour clock time of each sampling will be recorded.

Immunogenicity will be assessed using a validated ligand-binding assay designed to detect and titer ADA in the presence of LY3298176 at a laboratory approved by the sponsor. Confirmed positive samples for LY3298176 ADA will be titrated and then evaluated for cross-reactive binding to native GIP and GLP-1 using a validated ligand-binding assay. They may also be tested for their ability to neutralize the activity of assigned treatment (LY3298176-neutralizing antibodies) in separate cell-based neutralizing assays over-expressing the GIP and GLP-1 receptors. Antidrug antibody samples that test positive for neutralizing activity against LY3298176 and/or for cross-reactive binding to native GIP and GLP-1 may then be further tested for neutralizing activity against native GLP-1 and GIP using cell-based neutralizing assays.

All patients will have an ADA sample measured at ET or at the follow-up visit (Visit 801) approximately 1 month after the last dose of LY3298176. A risk-based approach will be used to monitor patients who have clinically significant treatment-emergent antidrug antibodies (TE-ADA) at the last visit. Treatment-emergent ADA are defined as those with a titer 2-fold (1 dilution) greater than the minimum required dilution if no ADA were detected at baseline or those with a 4-fold (2 dilutions) increase in titer compared to baseline if ADA were detected at baseline. Clinically significant TE-ADA will be defined as any TE-ADA at the follow-up visit (Visit 801) with:

- A high titer (≥ 1280) or an increasing titer from last measured value

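### The table of allergic-type events by TE-ADA status counts antibody samples that only patients with a drug hypersensitivity reaction give, and does not separate events that came before the antibodies (minor)

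*SAP*

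**What the plan says.** Four pieces of text combine.

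- **Sampling.** Protocol 9.10 sets routine sampling: "A blood sample will be collected at specific study visits according to the Schedule of Activities". The immunogenicity row of that schedule has one baseline sample (Visit 3) and four later ones (Visits 6, 8, 10 and 801, at Weeks 4, 8, 12 and 15), with a sample at early termination for those who leave. The same section adds: "In the event of drug hypersensitivity reactions (immediate or nonimmediate), additional samples will be collected as close to the onset of the event as possible", then "at the resolution of the event, and 30 days following the event".
- **Which samples count.** SAP 6.11.2.2: "Postbaseline period observations for each patient include all observations after the first administration of study drug". Nothing sets triggered samples aside.
- **The positive rule.** For a patient without antibodies at baseline, SAP 6.11.2.3 asks for "at least 1 postbaseline status of ADA Present with titer" at or above the threshold. A patient with antibodies at baseline likewise needs one sample with a 4-fold rise. The only restriction to pre-dose samples is in the Inconclusive rule ("postbaseline samples, drawn pre-dose, are ADA Inconclusive and all remaining postbaseline samples are ADA Not Present").
- **The table.** SAP 6.11.2.4: "A summary will be provided of the number and percentage of LY-treated patients experiencing specific TEAE", with the Table 6.8 events broken down by patient TE-ADA status. These are the anaphylaxis, hypersensitivity and angioedema queries and the injection-site and infusion-site reaction terms. No rule covers the origin of the samples or the order of event and antibody. A companion listing sets TEAEs beside the dated antibody results, with flags on qualifying samples, for every patient with antibodies or with a Table 6.8 event.

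**The concern.** The outcome affects how often the grouping variable is measured. A patient with a drug hypersensitivity reaction has more chances to meet an ever-positive rule than a patient without one, and the table then compares event percentages across the groups that the rule forms.

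A second and separate fault is order. The first scheduled postbaseline sample is at Week 4, and status is fixed over the whole postbaseline period. A reaction in the first weeks is counted as an event in a TE-ADA+ patient if antibodies appear only later.

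This is the only summary table planned to relate antibodies to allergic-type events, so a difference between its columns is likely to be read as information about immunogenicity.

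**Working it through.** The plan states no figure on this point, so there is none to reproduce. Every calculation assumes **no true association** between antibodies and events.

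**Inputs from the documents**
- Scheduled postbaseline samples for a completer: 4 (Schedule of Activities).
- Extra samples per drug hypersensitivity reaction: 3 (Protocol 9.10), so up to 4 + 3 = 7.
- LY-treated patients: 3 × 23 = 69 (Protocol synopsis).

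**Assumed, because the documents are silent:** event risk 6% or 10%; per-sample chance p of a qualifying result 2% to 30%; within-patient correlation; antibody duration and detection.

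**1. Independent samples (an extreme, since antibodies do not reset between draws).** P(TE-ADA+) = 1 − (1 − p)^k, with k = 4 or 7.
- p = 2%: 7.8% against 13.2%, odds ratio (OR) 1.80.
- p = 5%: 18.5% against 30.2%, OR 1.90.
- p = 10%: 1 − 0.9^4 = 34.4% against 1 − 0.9^7 = 52.2%. OR = (0.522/0.478)/(0.344/0.656) = 2.08. At 10% event risk the table would show events in 0.1 × 0.522/(0.1 × 0.522 + 0.9 × 0.344) = 14.4% of TE-ADA+ patients and 7.5% of TE-ADA- patients.
- p = 20%: 59.0% against 79.0%, OR 2.61.

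**2. Correlated samples (exchangeable latent normal).**
- p = 10%, correlation 0.5: 25.9% to 34.5%, OR 1.51.
- p = 10%, correlation 0.95: 14.3% to 16.0%, OR 1.14.
- p = 20%, correlation 0.8: 34.3% to 40.0%, OR 1.27.
- p = 30%, correlation 0.5: 59.0% to 69.6%, OR 1.59.

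**3. Time course (simulation, 1,000,000 patients per case).** Antibodies in 30% of patients, with onset uniform over Weeks 1-15. Events in 10%, uniform over Weeks 0-12. Triggered samples at onset, one week later and 30 days after onset.

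| Antibody course and retention | OR, all samples | OR, scheduled only |
|---|---|---|
| Mean 1 week, all stay | 1.37 | 1.00 |
| Mean 2 weeks, all stay | 1.23 | 1.00 |
| Mean 4 weeks, all stay | 1.14 | 1.01 |
| Persistent, 50% detection per sample, all stay | 1.12 | 1.00 |
| Persistent, perfect detection, all stay | 0.99 | 0.99 |
| Mean 2 weeks, half of event patients leave | 0.95 | 0.66 |
| Mean 2 weeks, all event patients leave | 0.72 | 0.36 |

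**4. Size in patients.** Expected number moved into TE-ADA+ = 69 × event risk × (P with 7 samples − P with 4).
- Correlated samples, 6% risk (69 × 0.06 = 4.1 event patients): 4.14 × 0.086 = 0.36 at p = 10% and correlation 0.5. Over p of 10% to 30% and correlation of 0.5 to 0.95 the range is 0.07 to 0.44.
- Independent samples, 6% risk: at most 4.14 × 0.200 = 0.83. At 10% risk the same extreme gives 6.9 × 0.200 = 1.4.

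**5. Order.** If patients with and without events have the same chance of being classified TE-ADA+, the event percentage is the same in both columns, whichever came first. Ignoring order therefore adds nothing to the null OR, as the scheduled-only column shows under full retention. It does affect attribution. In the full-retention cases, 57% to 68% of patients who had both an event and TE-ADA+ status had the event before antibody onset. Those percentages follow from the assumed timing.

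**The case against.** The strongest reply is that this is a descriptive exploratory table with no test and about four event patients at a 6% event rate. The listing lets each case be read in order, and a reaction before Week 4 has its own onset sample. That stands, and it is why the point is minor. The listing does not, however, correct the summary percentages.

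Second, seven samples is a maximum. The trigger is a drug hypersensitivity reaction, whereas Table 6.8 uses narrow or broad queries. Query hits not judged to be drug reactions trigger nothing. Injection site reactions are not named as a trigger, and under Protocol 9.2.1.2.2 they need not be recorded as AEs unless serious. All of this dilutes the effect, and it stands.

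Third, the direction is not fixed. Protocol 8.1.1 asks patients who stop study drug to remain, but Protocol 5.1 lets those unwilling to continue finish with an early termination visit. If many event patients leave, the OR falls below 1. This stands as a condition on the claim.

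Fourth, triggered samples exist to show whether antibodies accompany a reaction. Dropping them would label a patient who is positive only at the reaction as TE-ADA-. This also stands: scheduled-only status should not replace the all-samples version, and it is itself biased downward if event patients leave.

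**Conclusion.** The sampling fault follows from the text. As written, triggered samples count toward TE-ADA status, and one qualifying sample is enough. With retention, extra samples can only add patients with events to TE-ADA+, so any bias is toward an association. It needs transient or imperfectly detected antibodies. The documents allow for both: SAP 6.11.2.1 says drug in the sample can affect the assay, and Protocol 9.10 foresees titers returning to baseline. The null OR was about 1.0 to 2.6 with retention and 0.72 to 0.95 in the 2-week cases with withdrawal. The expected shift is under half a patient with correlated samples and a 6% event rate. It passes one patient only with independent samples and a 10% event rate.

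A reader might infer more, in three ways the documents do not support:
- **That the table will show an association whenever none exists.** It will not if antibodies persist and are well detected, and it may lean the other way if event patients leave.
- **That ignoring order adds to the spurious association.** It misattributes individual events, which is a different fault.
- **That a false immunogenicity signal for the compound is likely.** With so few expected events, the shift would be hard to see.

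**What to change.** In SAP 6.11.2.4:

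1. Keep the all-samples table. Beside it, give the same table with TE-ADA status from scheduled samples only (Visits 3, 6, 8, 10, and 801 or ET).
2. Identify patients who are TE-ADA+ only on an event-triggered sample.
3. Give the number of event patients who left before completing scheduled sampling, because neither version is unbiased if many did.
4. Split the events of TE-ADA+ patients into those starting before and those starting on or after the first TE-ADA+ sample.

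This needs SAP wording and a programming flag for scheduled against triggered samples; the event and sample dates are already planned data. The cost is a slightly larger descriptive table with small counts. Showing both versions avoids choosing between over-counting and hiding a patient who is antibody-positive only at the reaction.

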9.2.1.2.2. Injection Site Reactions

All injection site reactions, including reports of pain and burning, and information regarding their time of day, time relative to injection, size, amount of erythema, induration, and pruritus, as well as severity, will be recorded on specific eCRFs. In addition, if the reaction is clinically significant, the site should attempt to contact the sponsor for potential follow-up procedures. Injection site reactions do not need to be recorded as AEs unless they meet SAE criteria.

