- An association of TE-ADA with a moderate to severe injection site reaction or infusion-related reaction
- Cross-reactive and/or neutralizing binding of an ADA with endogenous GLP-1 or GIP.

Patients who have clinically significant TE-ADA should be followed with ADA testing every 3 months for approximately 1 year or until the ADA titers have returned to baseline ADA titer (defined as ADA titer within 2-fold of baseline). A PK sample may be collected at the follow-up immunogenicity assessment(s) if warranted and agreed upon between both the investigator and sponsor.

Every attempt should be made to contact patients for the follow-up immunogenicity assessment; however, if patients are unwilling or unable to return for the visit, this is not considered a protocol violation.

Patients followed for at least 1 year since last dose who have not returned to baseline, as defined above, will be assessed for safety concerns and, if no clinical sequelae is recognized by the clinical team, no further follow-up will be required.

Patients who have clinical sequelae that are considered potentially related to the presence of TE-ADA may also be asked to return for additional follow-up testing.

Samples will be retained for a maximum of 15 years after the last patient visit for the study, or for a shorter period if regulations and ERBs impose shorter time limits, at a facility selected by Lilly. The duration allows the sponsor to respond to future regulatory requests related to LY3298176. Any samples remaining after 15 years will be destroyed.

10. Statistical Considerations

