6.10.4. Adverse Events of Special Interest

Adverse events of special interest to be identified and described during this study are injection site reactions, hypersensitivity reactions, hypoglycemia, acute pancreatitis, major adverse CV events, and selected GI events (nausea, vomiting, and diarrhea).

Descriptive statistics for AESIs will be presented by treatment group and visit. Continuous responses will be summarized using sample size, mean, SD, median, minimum and maximum, while categorical responses will be summarized using sample size, frequency, and percentage.

In addition, for AESIs with information collected on the AE eCRF page (that is, hypersensitivity reactions, acute pancreatitis, and major adverse CV events) summary tables will be presented only if $>3\%$ of patients have the AESI. The incidence of patients with at least 1 AESI and the

patient incidence of AESIs will be summarized, showing frequency and percentage of patients, by SOC (if applicable), PT, and treatment group. The total number of AESIs and the number of AESIs for each SOC (if applicable) and PT will also be reported for each treatment group.

Listings by patient will be provided for AESIs. Listings will also present adjudication information by patient for adjudicated events.

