6.10.4.2. Injection Site Reactions

Injection site reactions are collected in a questionnaire. The following items or other available categories may be collected and summarized for each injection site reaction:

- pain
- itching
- rash
- reaction timing
- swelling
- redness
- erythema
- bruising
- hematoma

Injection site reactions which meet SAE criteria will also be collected as AEs. If >3% patients have such an event occur, then these injection site reactions may be summarized by PT using the version of MedDRA current at the time of programming.

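### The antibody-by-event table finds injection site reactions through coded adverse events, but only serious reactions must be entered as adverse events, so that row will probably be sparse and incomplete.

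*SAP*

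**What the plan says.** SAP 6.11.2.4 plans this output: "A summary will be provided of the number and percentage of LY-treated patients experiencing specific TEAE", split into TE-ADA positive, negative and inconclusive patients and ordered by preferred term. Table 6.8 defines the events. Three rows are standardized MedDRA queries (anaphylaxis, hypersensitivity, angioedema) and two are High-Level Terms. One of the two is "Events mapping to High-Level Term (HLT) of Injection site reaction". The same section plans a listing of treatment-emergent AEs beside antibody results, for any patient with antibodies present at any time or with a Table 6.8 event.

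Protocol 9.2.1.2.2 says that details of each injection site reaction, "as well as severity, will be recorded on specific eCRFs". It then states: "Injection site reactions do not need to be recorded as AEs unless they meet SAE criteria". SAP 6.10.4.2 agrees: "Injection site reactions are collected in a questionnaire", and "Injection site reactions which meet SAE criteria will also be collected as AEs". SAP 6.10.4 names the events of special interest that are held on the AE page ("that is, hypersensitivity reactions, acute pancreatitis, and major adverse CV events"), and injection site reactions are not among them.

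Protocol 9.10 gives one criterion for clinically significant TE-ADA as "An association of TE-ADA with a moderate to severe injection site reaction or infusion-related reaction".

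**The concern.** The row is defined by MedDRA coding, but most of the data it should count sit on a form for which no coding is described. A programmer following the SAP would query the coded AE records and find serious reactions plus whatever else sites had chosen to add. A near-empty row split by antibody status could then be taken as evidence that antibodies and local reactions are unrelated, when most of the reactions had not been drawn on.

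Severity makes this more than a matter of labels. A moderate or severe local reaction can fail every seriousness criterion in Protocol 9.2.1, so a site may leave it off the AE page. Yet Protocol 9.10 treats that type of reaction as relevant when it occurs with TE-ADA.

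**Working it through.** The plan states no figure on this point, so there is none to reproduce. The main check is to follow the data.

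1. Collection: all injection site reactions go to a dedicated eCRF with severity (Protocol 9.2.1.2.2), called a questionnaire in SAP 6.10.4.2.
2. Transfer to AE data: required only for serious reactions, by both documents.
3. Coding: SAP 6.10.4.2 mentions a preferred-term summary only for the serious reactions collected as AEs. No coding of questionnaire records is described.
4. Use: SAP 6.11.2.4 and Table 6.8 need a High-Level Term, which needs a coded record.

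No step carries a non-serious reaction from 1 to 4 unless a site also enters it as an AE.

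The other Table 6.8 rows are not shown to be affected. Protocol 9.2.1.2.3 has every hypersensitivity reaction reported as an AE or SAE.

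An illustration of scale follows. The protocol synopsis gives 23 patients per arm, so 3 × 23 = 69 on LY3298176. Let r be the share of these patients with a reaction, s the share of affected patients whose reaction is serious, and v the share of the non-serious ones that sites enter as AEs. All three are assumptions, because the documents give none of them.

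Expected patients in the row = 69 × r × [s + (1 − s)v]. The chance of at least one is 1 − (1 − p)^69, with p = r[s + (1 − s)v].

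With s = 1%:

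| r | Affected (69r) | In row, v = 0 | Chance of any | In row, v = 0.25 | Chance of any |
|---|---|---|---|---|---|
| 5% | 3.45 | 0.03 | 0.034 | 0.89 | 0.591 |
| 10% | 6.90 | 0.07 | 0.067 | 1.78 | 0.835 |
| 20% | 13.80 | 0.14 | 0.129 | 3.55 | 0.974 |
| 30% | 20.70 | 0.21 | 0.187 | 5.33 | 0.996 |

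With s = 5% and v = 0, the row expects from 0.17 patients (r = 5%) to about 1.0 (r = 30%).

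The fraction captured, s + (1 − s)v, does not depend on r. At s = 1% it is 1% for v = 0, 0.01 + 0.99 × 0.25 = 25.75% for v = 0.25, and 0.01 + 0.99 × 0.5 = 50.5% for v = 0.5. Capture therefore depends mainly on site habit, which the plan does not control.

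**The case against.** The strongest reply is that the source is unstated rather than wrong. The protocol's wording on injection site reactions is permissive, whereas for nausea, vomiting and diarrhea (9.2.1.2.1) and for hypoglycemia (9.2.1.2.4) it tells sites not to record non-serious events as AEs. The definitions of a treatment-emergent AE in Protocol Appendix 1 and SAP 6.10.3 name no eCRF page. SAP 6.10.4.3 even plans a listing of treatment-emergent gastrointestinal events although these have their own form.

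This stands in part. A reader might infer that the row must be empty whatever happens, or that the analysis has no data. The documents do not support either: sites may enter non-serious reactions as AEs, serious ones must be entered, and the full data exist on the eCRF. A reader might also infer that Table 6.8 decides who has clinically significant TE-ADA. It is not said to do so. Protocol 9.10 sets that status patient by patient, and Protocol 9.2.1.2 requires the sponsor to be alerted at once to any severe reaction, or to two or more moderate ones a week or more apart, serious or not.

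It is also fair to say that reactions are summarized by treatment group and visit and listed by patient (SAP 6.10.4, 6.10.4.2), and that the antibody listing already selects every patient with antibodies present. But those summaries are not split by TE-ADA status, the listing shows only treatment-emergent AEs, and the further immunogenicity analyses allowed at the end of 6.11.2.4 are optional. None of these completes the row.

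**Conclusion.** The mismatch is in the text and the SAP does not resolve it. Followed as written, the injection site row will probably show few reactions, and those shown will be an incomplete set that depends on voluntary AE entry. The documents give no reason to expect sites to enter reactions differently by antibody status, so the main effect is loss of events, not a bias of known direction.

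The consequence is limited. It concerns one row of a descriptive table under the exploratory analyses, plus the matching listing. In the listing, patients with antibodies present are still selected but some of their reactions would not appear. Patients who never have antibodies present would not be selected on the strength of a reaction that was not entered as an AE. The primary endpoint is untouched.

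The number of patients lost cannot be stated, because the documents give no reaction rate, no serious fraction and no rate of voluntary entry. The conclusion rests on there being no unwritten step that codes the questionnaire records and adds them to the treatment-emergent AE data. If one exists, a sentence in the SAP settles the matter.

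**What to change.** In SAP 6.11.2.4 and Table 6.8, replace the injection site row with: number and percentage of LY3298176-treated patients with at least one treatment-emergent injection site reaction, taken from the injection site reaction eCRF or from an AE coded to that High-Level Term, each patient counted once. Add a second row for patients with at least one moderate or severe reaction, using the severity recorded under Protocol 9.2.1.2.2. SAP 6.10.4.2 does not name severity among its questionnaire items, so the variable should be identified.

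Show both rows outside the preferred-term ordering unless the eCRF records are MedDRA-coded. Include the eCRF reactions in the listing of events beside antibody results, both as displayed events and as a reason for selecting a patient.

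The cost is SAP wording, a small amount of extra programming, and either coding or a separate display for the questionnaire records. No new data and no protocol change are needed. The Schedule of Activities already has injection site reactions evaluated at every site visit from Visit 3, at follow-up and at early termination.
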